9 STUDY ASSESSMENTS AND PROCEDURES

All study assessments and procedures will be performed at the time points presented in the schedules of assessments ([Table 1](#), [Table 2](#), [Table 3](#)). Descriptions of all clinical and laboratory evaluations are presented in [Section 10](#).

9.1 Screening

Testing will be done according to eligibility criteria and clinical assessment at screening. Screening evaluations for specific eligibility criteria must be completed within 30 days prior to enrollment for the given parameter but may be repeated as needed to confirm eligibility. If consent is obtained, the screening procedures indicated in the eligibility criteria will be undertaken. To avoid unnecessary additional venipuncture, if the appropriate blood test results for screening are available for the same subject (e.g., recent doctor's visit), these results may be used for assessing eligibility provided the results date is within the 30 days preceding enrollment to this trial.

Abnormal clinical findings from the medical history, physical examination, or blood tests at screening will be assessed. If a test is deemed clinically significant, it may be repeated to ensure it is not a single occurrence. If an abnormal finding is deemed to be clinically significant, the subject will be informed and referred for appropriate medical care with the permission of the subject. Decisions to exclude the subject from enrolling in the trial or to withdraw a subject from the trial will be at the discretion of the investigator.

Any study subject who has not yet received the current year influenza vaccination may receive this, if available, during the screening period but not within 14 days before or after study treatment start.

9.2 Protocol Deviations

A protocol deviation is any noncompliance with the clinical trial protocol, any process that is noted in the protocol and refers to details in the protocol-specific MOP or Good Clinical Practice (GCP) requirements, or any critical study procedures with specific instructions in ancillary documents referenced in the protocol such as a protocol-specific MOP.

The non-compliance may be either on the part of the subject, the participating site's PI, or the study staff. Following a deviation(s), corrective actions should be developed by the participating sites and implemented promptly. All individual protocol deviations will be addressed in subject study records.

It is the responsibility of each site's PI and study staff to use continuous vigilance to identify and report protocol deviations within 5 working days of identification of the protocol deviation, or within 5 working days of the scheduled protocol-required activity. All deviations must be promptly reported to Gritstone per the protocol deviation reporting procedures. Protocol deviations must be sent to the EC per their guidelines. The participating site's PI and study staff are responsible for knowing and adhering to the EC requirements.

10 DESCRIPTION OF CLINICAL AND LABORATORY EVALUATIONS

10.1 Clinical Evaluations

Complete medical history will be obtained by interviewing the subjects at the screening visit. Subjects will be queried regarding a history of significant medical disorders of the head, eyes, ears, nose, throat, mouth, cardiovascular system, lungs, gastrointestinal tract, liver, pancreas, kidney, urologic system, nervous system, blood, lymph nodes, endocrine system, musculoskeletal system, skin, and genital/reproductive tract. A history of any allergies, clotting or other abnormality of the coagulation system, cancer, immunodeficiency, psychiatric illness, substance abuse, and autoimmune disease will be solicited. At follow-up visits after the screening visit, an interim medical history will be obtained by interview of the subjects noting any changes since the previous clinic visit, phone call, or other form of contact. The interim medical history should include an assessment for new medical conditions and symptoms suggestive of an autoimmune disorder.

Concomitant medications will be collected as described in [Section 10.1.1](#).

At the screening visit (Visit 00), a physical examination will be performed by a study clinician licensed to make medical diagnoses. On Day 1 (Visit 01) prior to GRT-R910 vaccination and at follow-up visits after the initial GRT-R910 vaccination, a targeted physical examination may be performed by a study clinician licensed to make medical diagnoses, if indicated based on subject's interim medical history.

Vital signs (oral temperature, pulse, and blood pressure) will be collected at each study visit. Vital signs assessed on Day 1 prior to the first study vaccination will be considered as baseline. Subjects must not eat or drink anything hot or cold within 10 minutes prior to taking oral temperature.

WOCBP must have a negative urine or serum pregnancy test at screening for eligibility purposes for Cohort 6.

Height and weight will be collected on the screening visit to determine body mass index (BMI).

Electrocardiograms (ECGs) will be performed at the time points presented in the Schedule of Assessments ([Table 2](#) and [Table 3](#)). The ECG data will include heart rate and RR, PR, QT, and QRS durations. The investigator will be responsible for providing the interpretation of clinical significance for all ECG results.

Pre-administration reactogenicity assessments will be performed prior to each study vaccination to establish baseline, then the study vaccination will be given.

Subjects will be observed in the clinic for at least 45 minutes after GRT-R910 vaccination. The vaccination site will be examined, post-administration reactogenicity assessments will be performed, and any AE/SAEs will be assessed and recorded on the appropriate data collection form prior to discharge from the clinic. AESIs, including serologically or virologically confirmed SARS-CoV-2 infection and severity of COVID-19, PIMMCs, MAAEs, and NOCMCs will be collected from the time of first vaccination throughout the entire study. Any SAE occurring after signing of the ICF will be recorded and reported to the sponsor or designee by the investigator

within 24 hours of becoming aware of the SAE. If the SAE occurs after signing of the ICF and before the first (prime) dose, it will be reported on the medical history electronic case report form (eCRF). If the SAE occurs after the first (prime) dose, it will be reported on the AE eCRF.

All subjects will complete a subject memory aid through 7 days after each GRT-R910 vaccination. Subject memory aids will be reviewed with the subjects for AEs (solicited local and systemic reactions and unsolicited AEs) during telephone, e-mail, or text contacts or at a clinic visit, as appropriate.

Reactogenicity assessments will include an assessment of solicited AEs occurring from the time of GRT-R910 vaccination on Day 1 through Day 8 after GRT-R910 vaccination, which includes an assessment of local reactions including erythema (redness), induration (hardness)/edema (swelling), pain, and tenderness as well as systemic reactions including fever, chills (feverishness), fatigue (tiredness), malaise (general unwell feeling), myalgia (body aches/muscular pain exclusive of the injection site), arthralgia (joint pain exclusive of the injection site), headache, and nausea.

10.1.1 Assessment of Concomitant Medications/Treatments Other Than Study Product

Administration of any medications, therapies or vaccines will be recorded on the appropriate DCF. Concomitant medications will include all current medications and medications taken in the 30 days prior to signing the ICF for the duration of the study. Medications reported in the eCRF are limited to those taken within 30 days prior to the first study vaccination and for 12 months after GRT-R910 vaccination. Prescription and over-the-counter drugs will be included as well as herbals, vitamins, and supplements. In addition, receipt of any non-study vaccines will be solicited for the entire duration of the study and reported in the eCRF. Use of a new medication should prompt evaluation for the occurrence of any medication associated adverse effects, including a new diagnosis of chronic medical disease or condition.

Medications that might interfere with the evaluation of GRT-R910 should not be used during the trial reporting period (until approximately 12 months after GRT-R910 vaccination) unless clinically indicated as part of the subject's health care. Medications in this category include the prohibited medications per the Subject Exclusion Criteria (see [Section 7.2](#)). In addition, the site's PI or appropriate sub-investigator may identify other medications that should not be used due to a risk to subject safety or assessment of reactogenicity and immunogenicity.

10.1.2 Assessment of Subject Compliance With Study Intervention/Investigational Product/Investigational Device

Subjects will be directly observed at the time of dosing by a member of the clinical research team who is licensed to administer the study product. Administration will be documented on the appropriate data collection form and entered into the eCRF.

10.2 Laboratory Evaluations

10.2.1 Clinical Laboratory Evaluations

Subjects will be screened for HIV, hepatitis B surface antigen, antibody to hepatitis C virus and SARS-CoV-2. Results will be discussed with the subject. If a positive result occurs, the subject

will be referred for appropriate follow-up, and results will be reported as required by state law. These screening tests must be negative for the subject to be eligible to participate.

In order to be eligible for participation in the study and receipt of GRT-R910, the subject's clinical screening laboratory evaluations prior to each vaccination must be confirmed to meet the eligibility criteria as outlined in the Subject Inclusion Criteria (see [Section 7.1](#)).

The following tests will be performed by the local laboratory: WBC, Hb, PLT, ALT, AST, ALP, total bilirubin, CK, creatinine, PT/INR, aPTT, HIV serology, hepatitis B surface antigen, and hepatitis C antibody. Venous blood samples (approximately 17 mL) will be collected from each subject at the Screening Visit (Visit 00).

Clinical safety laboratory parameters evaluated after receipt of GRT-R910 will include WBC, Hb, PLT, ALT, AST, ALP, total bilirubin, CK, and creatinine.

Cardiac biomarker assessments will be performed for Cohorts 1 and 2 (subjects receiving booster dose) and Cohorts 3 and 4, and 6 to assess the potential risk of myocarditis with GRT-R910. Cardiac biomarker assessments include troponin T, C-reactive protein (CRP), and erythrocyte sedimentation rate (ESR).

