- If within 7 days after vaccination
- If prior to Visit 05
- Can be phone, text, or e-mail contact
- A nasal swab for SARS-CoV-2 should be performed within 3 days of COVID-19 symptoms and repeated after 7 days.
- AESIs, including serologically or virologically confirmed SARS-CoV-2 infection and severity of COVID-19, PIMMCs, MAAEs, and NOCMCs will be collected from the time of first vaccination throughout the entire study.
- SAEs occurring after signing of the informed consent form (ICF) will be recorded and reported to the sponsor or designee by the investigator within 24 hours of becoming aware of the SAE.

Table 2 Schedule of Assessments: Cohorts 1 and 2 – Subjects Receiving Booster Dose

Study Visit	V00	V01	V02	V03	V04	V05	V06	V07	V08	V09	V10	V11	V12	V13	V14	Unsch Visit	Early Term Visit
Study Day(s)	SCR -30 to -1	Day 1	Day 2 +1d	Day 4 +2d	Day 8 +2d	Day 29 ±3d	Day 57 ±3d	Day 113 ¹² -3d/+21d	Day 114 +1d	Day 116 +2d	Day 120 +2d	Day 142 ±3d	Day 170 ±3d	Day 293 ±3d	Day 478 ±7d		
Obtain Written Informed Consent	X																
Review Eligibility Criteria	X	X						X									
Medical History	X																
Review of Interim Medical History		X	X	X	X	X	X	X	X	X	X	X	X	X	X	X	X
Concomitant Medications	X	X	X	X	X	X	X	X	X	X	X	X	X	X	X	X	X
Vital Signs (Oral Temp, Pulse, BP)	X	X			X	X	X	X			X	X	X	X	X	X	X
Physical Examination Including Height and Weight	X																
Targeted Physical Examination, if Indicated		X			X	X	X	X			X	X	X	X	X	X	X
ECG ⁸		X ⁹			X	X	X	X ⁹			X	X	X	X	X		
Cardiac Biomarkers (Troponin T, CRP, ESR) ¹⁰		X ¹¹			X	X	X	X ¹¹			X	X	X	X			
Nasal Swab Collection for SARS-CoV-2 PCR	X															X ⁷	
Blood Collection for Safety Labs	X ¹				X ²		X ²				X ²		X ²	X ²		X ²	X ²
Blood Collection for HBsAg, Anti-HCV, SARS-CoV-2 Serology ³ , HIV	X						X ³						X ³				

Study Visit	V00	V01	V02	V03	V04	V05	V06	V07	V08	V09	V10	V11	V12	V13	V14	Unsch Visit	Early Term Visit
Study Day(s)	SCR -30 to -1	Day 1	Day 2 +1d	Day 4 +2d	Day 8 +2d	Day 29 ±3d	Day 57 ±3d	Day 113 ¹² -3d/+21d	Day 114 +1d	Day 116 +2d	Day 120 +2d	Day 142 ±3d	Day 170 ±3d	Day 293 ±3d	Day 478 ±7d		
Blood Collection for Cellular Immune Assays		X			X	X		X				X		X	X	X	X
Blood Collection for Antibody Assays		X				X	X	X				X		X	X	X	X
Vaccination		X						X									
45 Minute Evaluation After Study Vaccination		X						X									
Distribute Memory Aid and Study-Related Materials		X						X									
Review Memory Aid			X	X	X				X	X	X				X ⁴	X ⁴	
Adverse Events		X	X	X	X	X		X	X	X	X				X ⁵	X ⁵	

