SAEs/AESIs Including PIMMCs/MAAEs/NOCMCs ¹³	X ¹⁴	X	X	X	X	X	X	X	X	X	X	X	X	X	X	X	X
Phone Visit ⁶			X	X					X	X							
Saliva Collection for Antibodies		X			X			X			X			X			

Abbreviations: AESI, adverse event of special interest; BP, blood pressure; d, day(s); ECG, electrocardiogram; HBsAg, hepatitis B surface antigen; HCV, hepatitis C virus; HIV, human immunodeficiency virus; MAAE, Medically Attended Adverse Event; NOCMC, New Onset Chronic Medical Condition; SAE, serious adverse event; PCR, polymerase chain reaction; PIMMC, Potentially Immune-Mediated Medical Condition; SARS-CoV-2, severe acute respiratory syndrome coronavirus 2; SCR, screening; Unsch, unscheduled

- Includes white blood cells (WBCs), hemoglobin (Hb), platelets (PLT), alanine aminotransferase (ALT), aspartate aminotransferase (AST), alkaline phosphatase (ALP), total bilirubin, creatine kinase (CK), serum creatinine, prothrombin time (PT)/international normalized ratio (INR), and activated partial thromboplastin time (aPTT)
- Includes WBC, Hb, PLT, ALT, AST, ALP, total bilirubin, CK, and creatinine
- Includes SARS-CoV-2 serology (N-specific) only
- If within 7 days after each vaccination (prime or boost dose)

- 5 If prior to Visit 11
- 6 Can be phone, text, or e-mail contact
- 7 A nasal swab for SARS-CoV-2 should be performed within 3 days of COVID-19 symptoms and repeated after 7 days.
- 8 ECG will be performed for subjects receiving booster dose in Cohorts 1 and 2. ECG data will include heart rate and RR, PR, QT, and QRS durations.
- 9 ECG will be performed before 1st and 2nd doses of vaccination.
- 10 Cardiac biomarker assessment will be performed for subjects receiving booster dose in Cohorts 1 and 2. Cardiac biomarker assessments will include troponin T, C-reactive protein (CRP), and erythrocyte sedimentation rate (ESR).
- 11 Cardiac biomarker assessment will be performed before 1st and 2nd doses of vaccination.
- 12 In case of second dose delay (allowed -3 days/+21 days), all safety visits (Visit 08 to Visit 12) will be scheduled based on the day of the second dose (e.g., Visit 08 will occur 1 day after delayed second dose and not on Day 114). All visits will shift based on the second dose without changing the time interval between 2 consecutive visits.
- 13 AESIs, including serologically or virologically confirmed SARS-CoV-2 infection and severity of COVID-19, PIMMCs, MAAEs, and NOCMCs will be collected from the time of first vaccination throughout the entire study.

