Sexual abstinence is considered a highly effective method only if defined as refraining from heterosexual intercourse during the entire period of risk associated with the study treatments. The reliability of sexual abstinence needs to be evaluated in relation to the duration of the clinical trial and the preferred and usual lifestyle of the subject.

Note: Periodic abstinence (calendar, symptothermal, postovulation methods), withdrawal (coitus interruptus), spermicidal products, barrier methods (such as cervical sponge, diaphragm, or condom with spermicide), and lactational amenorrhea method (LAM) are not acceptable methods of contraception.

Note: Vasectomized male partner is considered a highly effective birth control method, provided that partner is the sole sexual partner of the female trial participant who is of childbearing potential and that the vasectomized male has received medical assessment of the surgical success.

10. WOCBP must have a negative urine or serum pregnancy test within 24 hours prior to each study vaccination.
11. Male subjects of childbearing potential must agree to the use of condoms to ensure effective contraception with a female partner from the time of study vaccination until 3 months after vaccination. Male subjects agree to refrain from sperm donation from the time of first vaccination until 3 months after the last vaccination. Male subjects of childbearing potential are biological males who are post-pubertal and considered fertile until permanently sterile by bilateral orchiectomy or vasectomy.
12. Plan to remain living in the area for the duration of the study.
13. Clinical screening laboratory evaluations: white blood cells (WBCs), hemoglobin (Hb), platelets (PLT), alanine aminotransferase (ALT), aspartate aminotransferase (AST), alkaline phosphatase (ALP), total bilirubin, creatine kinase (CK), serum creatinine, prothrombin time (PT)/international normalized ratio (INR), and activated partial thromboplastin time (aPTT) are within normal reference ranges at the clinical laboratory being used, with the exception that ALT, AST, ALP, and creatinine values that are below the reference range will not be exclusionary as these values below reference range are clinically insignificant. Any other screening laboratory value outside the reference range that is thought to be clinically insignificant by a site investigator must be discussed with Gritstone's Medical Officer prior to enrollment.

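### Laboratory eligibility is a condition of every dose, but boosted Cohorts 1 and 2 have no safety laboratory draw scheduled between Day 57 and the Day 113 booster

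*Protocol*

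**What the plan says.** **The condition.** Protocol 10.2.1 ties receipt of GRT-R910 to laboratory eligibility: the subject's "clinical screening laboratory evaluations prior to each vaccination must be confirmed to meet the eligibility criteria" in Section 7.1. Criterion 13 there names 11 items (WBC, Hb, PLT, ALT, AST, ALP, total bilirubin, CK, creatinine, PT/INR, aPTT) and requires that they "are within normal reference ranges at the clinical laboratory being used", with limited exceptions. Section 7.2 adds that no exemptions from the criteria are granted.

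**The schedule.** In Protocol Table 2 (Cohorts 1 and 2, boosted), the row "Review Eligibility Criteria" is marked at screening, Day 1 and V07. The row "Blood Collection for Safety Labs" is marked at screening, V04 (Day 8), V06 (Day 57), V10 (Day 120), V12 and V13, plus unscheduled and early termination visits. It is blank at V07. SAP Table 7 is also blank there.

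**The panel.** After screening, footnote 2 applies: "Includes WBC, Hb, PLT, ALT, AST, ALP, total bilirubin, CK, and creatinine". That is 9 items, without coagulation. Section 10.2.1 gives the same list: "Clinical safety laboratory parameters evaluated after receipt of GRT-R910 will include WBC, Hb, PLT, ALT, AST, ALP, total bilirubin, CK, and creatinine".

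**The booster window.** Footnote 12 of Table 2 reads "In case of second dose delay (allowed -3 days/+21 days), all safety visits (Visit 08 to Visit 12) will be scheduled" from the day of the second dose. It does not move V06.

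**The concern.** A site that follows Table 2 exactly reaches the booster visit, reviews eligibility, and has no laboratory value from the preceding seven weeks to review. Section 10.2.1 does not say which result counts before dose 2 or how old it may be. No scheduled draw after the prime covers all of criterion 13.

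This concerns dose 2 in adults aged 60 or over, including the only 30 mcg cohort. CK and platelets are among the missing values. Section 7.2.3 itself gives missed safety laboratory tests as an example of increased risk. The halting criteria in 11.6.1 count related Grade 3 laboratory abnormalities after booster dosing. Without a value shortly before dose 2, an abnormal Day 120 result is harder to place before or after that dose, which makes the relatedness judgement less secure.

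**Working it through.** The plan states no figure on this point, so there is none to reproduce. The check reads the table rows and does day arithmetic on the visit windows.

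**1. Latest scheduled draw before the booster, Cohorts 1 and 2 (Protocol Table 2)**
- V06: Day 57 ±3, so Days 54 to 60.
- V07: Day 113 −3/+21, so Days 110 to 134.
- Scheduled safety draws after V06, up to and including V07: 0.

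**2. Age of that result at the booster (booster day − draw day)**
- Nominal: 113 − 57 = 56 days.
- Shortest: 110 − 60 = 50 days.
- Longest: 134 − 54 = 80 days.

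**3. Completeness of the panel**
- Criterion 13: 11 items. Footnote 2 panel: 9 items. Difference: 2 items, PT/INR and aPTT.
- Their only scheduled draw is at screening, Day −1 at the latest. The SAP has no Day 0, so Day −1 is 1 day before Day 1. At the earliest booster the coagulation result is then at least 1 + (110 − 1) = 110 days old.

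**4. Blood already taken at V07 (Protocol Table 2)**
- Three rows are marked: cardiac biomarkers, cellular immune assays, and "Blood Collection for Antibody Assays".

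**5. Context only: Cohorts 3, 4 and 6 (SAP Table 8)**
- The safety laboratory row has a mark at V06 (Day 29), their booster visit.
- Without that mark, the previous draw would be V04 (Day 8 +2, so Days 8 to 10). Against V06 (Day 29 ±3, so Days 26 to 32) its age would be 29 − 8 = 21 days nominal, 26 − 10 = 16 at the shortest and 32 − 8 = 24 at the longest.
- So the schedule with the longer interval is the one without a booster-visit draw. The weight of this comparison is discussed under the objection.

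**6. Number of subjects**
- Ceiling: 10 + 10 = 20. Fewer if some declined the booster, which needed a separate consent (SAP 7.2).

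**Reading note.** In the text read from SAP Table 7, the later marks in this row are shifted by one column relative to Protocol Table 2. V07 is blank in both. The finding rests on Protocol Table 2.

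**The case against.** **Day 57 is before the booster.** This stands. Section 10.2.1 asks for results before each vaccination, not at the visit, and sets no maximum age. A site could comply literally by confirming the Day 57 panel at V07. A reader might infer that dose 2 is given in breach of the protocol, but the documents do not show that. Nor is the 30-day limit in 9.1 breached, because it is written for enrollment. Section 11.3.1 also refers eligibility questions to the manual of procedures, which was not available and may settle this. What remains is that no text names Day 57 as the pre-booster check.

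**Coagulation at screening only looks intended.** This largely stands, since 10.2.1 and footnote 2 give the same 9-item list. The remedy there is wording, not an extra test.

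**The comparison with Cohorts 3, 4 and 6 is weak.** This stands too. It rests on one SAP Table 8 mark that, unlike the others in its row, has no panel footnote. As extracted, the same table puts its third eligibility-review mark at Day 30, not at the Day 29 dosing visit, so column positions there are uncertain. The matching row of Protocol Table 3 is not in the text. The table does not say whether the Day 29 result is available before dosing. A reader might infer that those cohorts meet 10.2.1 and Cohorts 1 and 2 do not; the documents do not support that.

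**There are other safeguards.** Table 2 requires an ECG and cardiac biomarkers (troponin T, CRP, ESR) before dose 2, with an interim history and, if indicated, a targeted examination at V07. Acute illness defers dosing. These narrow the gap but give no current CK, platelet or liver value.

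**The boosters may be finished.** This is possible. The SAP describes booster consent in the past tense, and it dates the protocol version to February 2023. The fix allows for it.

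**Conclusion.** The point holds as a modest safety and consistency gap. The protocol makes each dose conditional on laboratory eligibility, but for boosted Cohorts 1 and 2 its schedule yields only a result 56 days old (50 to 80) at dose 2, without the two coagulation items, in at most 20 subjects.

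This assumes that Table 2 is the operative schedule, that no unscheduled draw fills the interval, and that the manual of procedures does not already name a qualifying result.

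Two further inferences should be resisted. The primary laboratory endpoint is not compromised, because SAP 4.2 takes baseline as the last value on or before the prime. And the raised CK in 3 patients in Protocol 4.3.3 is not evidence of risk here: they were cancer patients on checkpoint inhibitors, in studies using SAM doses of 30 to 300 mcg. It is a reason to look at CK before dose 2, no more.

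**What to change.** **If boosters remain to be given.** Add the 9-item safety panel to Protocol Table 2 and SAP Table 7 at V07, or within a short stated window before it, with results reviewed before dose 2. Amend 10.2.1 to say that this panel is the pre-booster check, how old a qualifying result may be, and that coagulation is checked at screening only. The age of the latest result then falls from 56 days to 0, or to the chosen lead time.

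**If Cohort 1 and 2 boosters are complete.** Correct the 10.2.1 wording, list the date and result of each boosted subject's last laboratory evaluation before dose 2, and state whether it is handled as a protocol deviation.

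**Cost.** A small extra blood volume in at most 20 subjects; the documents give no volume for this panel. A draw at V07 itself needs no added venepuncture, because blood is already taken there. Laboratory turnaround is not stated, so if same-day results are not available, reviewing them before dosing would need a short extra draw before V07. If the boosters are complete, the cost is one wording change and one listing.
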